9.0 Study Withdrawal/Discontinuation

Subjects will be free to withdraw from the study at any time, which will be made clear at enrollment. Subjects will be withdrawn from the study if:

- Pregnancy is detected
- The PI's medical judgement is that participation places the subject at risk for harm

10.0 Statistical Considerations

- Sample size: The sample size in this cross-sectional study design (10 per control group, 16 per T1DM group, and 10 per MODY2 group) was calculated to detect a 40% difference in mean glucose update (R_d) between MODY2 and T1DM subjects during maximal insulin stimulation (sample period 2) with an a-level of 5% and 80% statistical power. The R_d variance and R_d for well controlled T1DM subjects utilized in sample size calculations were taken from Bergmann et al. where a 55% difference in R_d was seen between T1DM and control groups.(10)
- Primary outcome: Differences in R_d during maximal insulin stimulation (sample period #2) between MODY2 and T1DM subjects will be evaluated using the Mann-Whitney U test, presuming a non-parametric distribution in the data. Differences in R_d between MODY2 and control subjects and between T1DM and control subjects will be similarly determined.
- Secondary outcome: The differences in suppression of glucose production (ΔR_a), suppression of NEFA, and suppression of glycerol between each of the 3 subject groups will be assessed using the Mann-Whitney U test as for the primary outcome.
- Timeline and interim analysis: I plan to study 18 subjects in year 1 and 12 additional subjects in a second year of funding. One interim assessment of the

primary outcome (R_d) will be made after 5 studies per group before the end of the year 1 funding period. Obrien-Fleming bounds for a two-sided test with a-level of 5% and a critical z-value of 2.80 (corresponding to a p-value of 0.0051) will be used to assess whether the study can be ended at interim analysis if there were a large difference in R_d between T1DM and MODY2 groups. At this point I will also analyze the variance in R_d and adjust the sample size if needed for subsequent studies in year 2

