2.0 Rationale and Specific Aims

The following research plan will determine whether IR in T1DM is predominantly an effect of chronic hyperglycemia, as is commonly accepted,(17-22) or a consequence of iatrogenic hyperinsulinemia in the peripheral circulation, as I alternatively hypothesize. Despite its independent contribution to micro- and macrovascular disease,(14, 16, 24) the underlying cause of IR has not been established nor have strategies to mitigate it been developed.

Insulin therapy in T1DM attempts to achieve euglycemia but does so in an "unphysiologic" way, by delivering insulin into the subcutaneous tissue as compared to physiologic delivery directly into the hepatic portal circulation. Thus, peripheral insulin delivery must balance competing factors: 1) a sufficient amount of insulin must reach the liver to prevent unrestrained hepatic glucose production and resultant hyperglycemia and 2) simultaneously, an excess of insulin in the peripheral circulation must be avoided to prevent hypoglycemia, as I recently reported.(25) Although life-saving, peripheral insulin delivery in T1DM results in a loss of the normal insulin distribution; the physiologic state maintains insulin at 3-fold higher concentrations in the portal circulation compared with the peripheral circulation.(26-29) IR in T1DM could therefore occur in response to peripheral hyperinsulinemia, a mechanism that would protect against hypoglycemia and ensure adequate glucose delivery to the CNS.

This protocol is designed to test these hypotheses:

 IR in T1DM is a homeostatic response to increased peripheral insulin concentrations resulting from peripheral insulin delivery and *not* significantly attributable to hyperglycemia, and
 IR in T1DM results primarily from peripheral tissue IR (especially muscle) and *not*

primarily from hepatic IR.

Protocol Version #: 10 Protocol Date: October 24, 2017 To test this hypothesis, I plan to utilize the hyperinsulinemic, euglycemic clamp (insulin clamp) to assess IR in a cross-sectional study of 3 groups of subjects:

- 1) non-diabetic control subjects,
- 2) patients with well controlled T1DM, and
- 3) patients with glucokinase (GCK) mutations causing mature-onset diabetes of the young, type 2 (MODY2), a population that has hyperglycemia without hyperinsulinemia.

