As summarized in **Table 1** and discussed in the following proposal, key metabolic differences between these 3 groups will enable distinction to be made between the relative contributions of peripheral hyperinsulinemia vs. hyperglycemia to IR in T1DM.

Specific Aim 1: Determine whether whole-body IR in T1DM is secondary to

peripheral insulin delivery (as opposed to hyperglycemia). This study is designed to select T1DM subjects with matched glycemic control to that of MODY2 subjects. Importantly, because MODY2 patients retain pancreatic insulin secretion, the key factor influencing a difference in insulin sensitivity between these two groups will be that T1DM patients have iatrogenic peripheral hyperinsulinemia and portal hypoinsulinemia, while the insulin distribution remains normal in MODY2 (**Table 1**). Additionally, because there is no difference in insulin distribution between MODY2 and control subjects, the key factor influencing a difference in insulin sensitivity between these two groups is the presence of hyperglycemia in MODY2 and euglycemia in control.

Table 1: Key Between-Group Differences between control, MODY2, and T1DM subjects. Pe=peripheral, Po=portal. Shading is used to highlight similarities and differences between groups. Note: 1) MODY2 and T1DM subjects will be selected to have similarly mild hyperglycemia 2) Insulin distribution between peripheral and portal circulations will be normal in control and MODY2 subjects, but altered in T1DM.

Subject Group	Chronic Glycemia	Insulin Distribution	Risk of CAD	Muscle IR	Hepatic IR	Key Between-Group Differences Affecting IR
Control	Normal	Normal	Normal	Normal	Normal	Mild hyperglycemia
MODY2	\uparrow	Normal	Normal	Unresolved	Unresolved	Mild hyperglycemia AND Pe. hyperinsulinemia Pe. hyperinsulinemia
T1DM	\uparrow	Pe. hyperinsulinemia Po. hypoinsulinemia	$\uparrow\uparrow\uparrow$	$\uparrow\uparrow$	Unresolved	

Specific Aim 2: Establish the tissue-specific distribution of IR in T1DM

(muscle, fat, and liver). The tissue-specific site of IR in T1DM has not been well established. By utilizing a 2-step clamp procedure, I will be able to simultaneously assess whether T1DM IR is predominantly an effect of muscle IR (as I hypothesize) or whether hepatic IR also contributes to the whole body IR seen in this condition.

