IR is a consistent(8-12) and under-recognized finding in T1DM, even among patients who lack traditional IR risk factors (such as those commonly seen in type 2 diabetes). Because IR has been strongly and independently correlated with macrovascular disease in T1DM,(14-16) an increased understanding of its root cause is needed. While earlier investigations attributed T1DM IR to hyperglycemia, (17-22) more recent studies have shown little to no correlation between hyperglycemia and insulin sensitivity.(10, 11, 13, 23) Thus, the degree to which hyperglycemia contributes to IR in T1DM is unclear, and this uncertainty suggests that other factors contribute prominently. This study tests the hypothesis that *iatrogenic hyperinsulinemia* rather than *hyperglycemia* is the primary contributor to T1DM IR. To date only one study has examined pediatric T1DM patients with typical glycemic control, which found that adolescents were 37% less insulin sensitive than matched control subjects,(11) suggesting that exposure to IR begins early in the natural history of T1DM.

To determine the root cause of T1DM IR and translate this information into therapies that would ameliorate IR in T1DM and its contribution to macrovascular disease, the mechanisms causing IR must be assessed *early in the disease duration*. This is because:

- T1DM IR appears to begin early in the disease process,(11, 17)
- the incidence of T1DM onset is highest between ages 10-14,(70) and
- 3) at younger ages and shorter disease durations there are minimal confounding covariables that would contribute to IR at a molecular level. These confounding covariables include co-morbidities associated with T1DM such as diabetic nephropathy,(71) prolonged exposure to hypertriglyceridema,(72, 73) excessive BMI(74, 75) and visceral adiposity,(76, 77), deleterious effects of aging and progressive inflammation on extracellular matrix remodeling,(78, 79) and increasing age per se.(80, 81)

By studying young patients early in the disease duration, this investigation will not only more precisely determine whether *iatrogenic hyperinsulinemia* or *hyperglycemia* is the key modifiable risk factor to address in alleviating

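### Aim 1 asks how much of T1DM insulin resistance is due to hyperglycemia, but the only MODY2-control analysis is a 10 v 10 Mann-Whitney test, which can neither show a small effect nor rank it against insulin distribution

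*Combined protocol and SAP*

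**What the plan says.** Section 2.0 opens by saying that the research "will determine whether IR in T1DM is predominantly an effect of chronic hyperglycemia" or of iatrogenic peripheral hyperinsulinemia. Hypothesis 1 has a positive and a negative half: insulin resistance in T1DM is a response to raised peripheral insulin "resulting from peripheral insulin delivery and *not* significantly attributable to" hyperglycemia. The three groups are meant to "enable distinction to be made between the relative contributions of peripheral hyperinsulinemia vs. hyperglycemia to IR in T1DM". Specific Aim 1 gives each pair a job. T1DM versus MODY2 isolates insulin distribution. For MODY2 versus control, the key factor "between these two groups is the presence of hyperglycemia in MODY2 and euglycemia in control". Section 7.6.1 restates the hypothesis as hyperinsulinemia "rather than *hyperglycemia* is the primary contributor to T1DM IR".

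Section 10.0 plans 10 control, 16 T1DM and 10 MODY2 subjects, sized for a 40% difference in R_d between MODY2 and T1DM (alpha 5%, power 80%). That contrast is tested with the Mann-Whitney U test. The other two pairs get one sentence: "Differences in R_d between MODY2 and control subjects and between T1DM and control subjects will be similarly determined". Section 10.0 names no effect estimate, confidence interval, margin or direct comparison of the two contributions, and no rule for reading a non-significant MODY2-control result.

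**The concern.** The conclusions that Aim 1 is meant to support concern size: the hyperglycemia contribution is small, or is the lesser of the two. The planned output for that half of the aim is a test of no difference. A non-significant result is compatible with no effect and with a substantial one. A significant result shows that there is some effect but not how it compares with the other.

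If both tests are significant, the plan has no way to say which contribution is larger. If only T1DM-MODY2 is significant, it is natural to conclude that insulin matters and hyperglycemia does not, yet that pattern can arise when the two contribute equally.

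**Working it through.** **Inputs.** From section 10.0: group sizes 10, 16 and 10; 40% difference; alpha 5% (two-sided is stated for the interim bounds and assumed elsewhere); power 80%. Section 10.0 also says that "The R_d variance and R_d for well controlled T1DM subjects utilized in sample size calculations" came from a cited clamp study "where a 55% difference in R_d was seen between T1DM and control groups". With control R_d set to 100, that puts T1DM at 45. Section 1.0 gives a range of 35-57% across clamp studies; its low end puts T1DM at 65. The SD, the mean R_d and the base of the 40% are not printed.

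**The plan's own figure.** The sizes 10 and 16 cannot be reproduced without the SD. This is no evidence that they are wrong. Working backwards, 10 v 16 has 80% power at a standardized difference of 1.177 (t test) or 1.225 (exact Mann-Whitney, simulated with normal data). Taking the 40% of the T1DM mean, with one common SD:
- T1DM = 45: difference 0.40 x 45 = 18; SD = 18/1.225 to 18/1.177 = 14.7 to 15.3.
- T1DM = 65: difference 0.40 x 65 = 26; SD = 26/1.225 to 26/1.177 = 21.2 to 22.1.

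**Precision of MODY2-control.** The t-based 95% half-width at 10 v 10 is 2.101 x sqrt(2/10) = 0.94 SD. That is 13.8-14.4 points (T1DM = 45) or 19.9-20.8 points (T1DM = 65).

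**A positive primary test does not settle the order.** With T1DM = 45 and a MODY2-T1DM difference exactly as sized:

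| Base of the 40% | MODY2 | Hyperglycemia (control - MODY2) | Insulin distribution (MODY2 - T1DM) |
|---|---|---|---|
| T1DM mean | 1.4 x 45 = 63 | 37 | 18 |
| MODY2 mean | 45/0.6 = 75 | 25 | 30 |
| Points of control | 45 + 40 = 85 | 15 | 40 |

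Either contribution may be the larger.

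**Joint behavior of the two tests.** Simulation with 40,000 trials per case, normal data and a common SD, ignoring the interim look. Exact rejection regions are U <= 23 (10 v 10) and U <= 42 (10 v 16). MODY2 is placed so that hyperglycemia causes a given share of the control-T1DM deficit. T1DM = 45:

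| Share due to hyperglycemia | Both significant | Only T1DM-MODY2 significant |
|---|---|---|
| One-third | 67-70% | 30-33% |
| One-half | 94-96% | 3-5% |
| Two-thirds | 78-82% | under 1% |

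The commonest pattern is the same in all three rows, so it does not tell them apart.

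**Frequency of the tempting pattern.** Under equal contributions, 'only T1DM-MODY2 significant' occurs in 3-5% of trials above and in about 35% if T1DM = 65. On other readings of the 40% or of the SD (one SD or constant CV), with T1DM = 45, it occurs in 33-52%. With T1DM = 65 and constant CV, 40% of the T1DM mean, it occurs in 43%. I dropped readings whose sizing assumption puts MODY2 above control (T1DM = 65: 65/0.6 = 108, or 65 + 40 = 105), because they leave no hyperglycemia deficit to apportion.

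**Direct contrast.** (MODY2 - T1DM) - (control - MODY2) = 2 x MODY2 - control - T1DM. SE = SD x sqrt(4/10 + 1/10 + 1/16) = 0.75 SD. The 95% half-width is t(33) x 0.75 SD = 2.035 x 0.75 SD = 1.53 SD, or 22-23 points (T1DM = 45) and 32-34 points (T1DM = 65). For comparison, if hyperglycemia causes one-third of a 55-point deficit, the true contrast is 55/3 = 18.3 points.

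**The case against.** The strongest reply is that the misuse is not in the text. No section says that a non-significant MODY2-control test will be taken as no effect, or that p-values will be ranked, and naming a test does not forbid reporting estimates. A reader might infer that the plan commits this error; the documents do not support that. What stands is narrower: hypothesis 1 has a negative half, and this test is the only analysis given for it.

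A second reply is that the insulin half is sound. T1DM-MODY2 is the sized contrast and the basis of the interim stop. That is correct, and nothing here weakens it.

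Third, the numbers rest on a back-solved SD. That is also correct. The timeline in section 10.0 totals 18 + 12 = 30 subjects rather than 10 + 16 + 10 = 36. If the power statement belonged to 10 per group, the standardized difference would be about 1.32 and the SD 18/1.32 = 13.6, smaller than used here. It is tempting to quote about 35% as the chance of a misleading result, but that figure needs T1DM = 65, which is not the 55% input that section 10.0 cites. The documents select no single frequency. The logical point needs no SD.

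Finally, side-by-side intervals do not rank two effects that share the MODY2 group. This is right, so the direct contrast has to be part of the fix.

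**Conclusion.** The concern holds in this form: for the hyperglycemia half of Aim 1, the planned 10 v 10 Mann-Whitney test cannot show that the effect is small, and the set of planned tests cannot show that it is smaller than the insulin-distribution effect. Confidence in this is high, because it follows from what a test of no difference can establish.

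The size is illustrative. It assumes normal data, a common SD backed out from the stated power, the 40% taken of the T1DM mean, and no interim stop. On that basis a MODY2-control interval reaches about 14 points of control R_d either side when T1DM = 45, or 20-21 when T1DM = 65. The p-value pattern carries some information at T1DM = 45, since 'only T1DM-MODY2 significant' becomes rarer as the hyperglycemia share rises, but in most trials it is the same for all three shares.

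A reader might go further and infer that the primary comparison is invalid or the sample size wrong. Neither follows. This is worth fixing before the interim look, but it does not threaten the powered comparison.

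**What to change.** Add to section 10.0, before the interim look at R_d:

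1. Report all three pairwise R_d differences with 95% confidence intervals beside the Mann-Whitney p-values. Use Hodges-Lehmann intervals, or mean differences allowing unequal variances if the group spreads differ (Hodges-Lehmann assumes a location shift).
2. Base any statement that the hyperglycemia effect is small on the MODY2-control interval, and state that a non-significant test alone is inconclusive.
3. Base any statement about which contribution is larger on the prespecified contrast 2 x MODY2 - control - T1DM with its 95% interval, not on separate p-values or side-by-side intervals. A positive value favors insulin distribution as the larger contribution.

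The cost is a few sentences. The tests, the sized contrast and the data collection stay as they are, and no subjects are added. The drawback is that the direct contrast is imprecise (1.53 SD either side), so the hyperglycemia half may more often have to be reported as inconclusive.

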12.0 Follow-up and Record Retention

The study is anticipated to last for two years. The study results will be maintained indefinitely for research purposes.

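### Section 10.0 gives two different planned totals: 36 subjects in the sample-size statement and 30 in the two-year schedule

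*Combined protocol and SAP*

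**What the plan says.** The sample-size bullet of section 10.0 gives the group sizes as "10 per control group, 16 per T1DM group, and 10 per MODY2 group". It says they were "calculated to detect a 40% difference in mean glucose update (R_d) between MODY2 and T1DM subjects" during maximal insulin stimulation, "with an a-level of 5% and 80% statistical power". The R_d mean for T1DM and the variance come from a cited study, and their values are not reproduced.

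The timeline bullet of the same section says "I plan to study 18 subjects in year 1 and 12 additional subjects in a second year of funding". It places one interim look at the primary outcome, which "will be made after 5 studies per group before the end of the year 1 funding period", and uses an O'Brien-Fleming bound with "a critical z-value of 2.80 (corresponding to a p-value of 0.0051"). After that look the investigator will examine the R_d variance and "adjust the sample size if needed for subsequent studies in year 2".

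Section 12.0 adds: "The study is anticipated to last for two years".

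**The concern.** The two bullets describe the same study and give different totals. The stated power belongs to one of them only. No third year is described in which six more subjects could be studied, and the 30 are not divided among the three groups.

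If 30 is the real target, the MODY2 v T1DM comparison may have less power than stated, by an amount that depends on the split. If 36 is the real target, the schedule is six subjects short. A reader cannot tell which applies.

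**Working it through.** **Totals (section 10.0).** Group sizes: 10 + 16 + 10 = 36. Schedule: 18 + 12 = 30. Difference: 6, and 6/36 = 17%.

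**Can the stated 80% be reproduced?** No, because the R_d mean and SD are not in the documents. The standardised difference d (the 40% difference divided by the SD) can only be back-solved by assuming that 80% is exact at 16 v 10. I took the test as two-sided; the plan says so for the interim bounds, and I assume it holds for the sample size too.

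**Back-solving d.** Two-sample t test, 24 degrees of freedom, noncentrality d / √(1/10 + 1/16). Setting power to 0.80 gives d = 1.177. The normal approximation gives (1.960 + 0.842) × √0.1625 = 1.129.

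**Power at 10 v 10 with that d.**

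| Method | d | 16 v 10 | 10 v 10 |
|---|---|---|---|
| Normal approximation | 1.129 | 80% | 71.4% |
| Noncentral t | 1.177 | 80% | 70.2% |
| Simulated exact Mann-Whitney, normal data | 1.23 | 80.3% | 69.3% |

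Mann-Whitney is the planned test. The three methods agree on about 70%.

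**Detectable difference at 10 v 10.** 80% power needs d = 1.325. With the SD unchanged, 1.325 / 1.177 × 40% = 45.0%.

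**Other splits of 30 (noncentral t, d = 1.177).** The best power for the primary contrast depends on how many controls are given up:

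| Controls | Left for MODY2 + T1DM | Best power |
|---|---|---|
| 10 | 20 | 70% |
| 9 | 21 | 72% |
| 8 | 22 | 75% |
| 7 | 23 | 77% |
| 6 | 24 | 79% |
| 5 | 25 | 80% |
| 4 | 26 | 82% |

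With MODY2 held at 10, reaching 80% takes 16 T1DM and leaves 4 controls. Within a total of 30, then, 80% is kept only by cutting controls to five or fewer. That would weaken the two comparisons with controls that section 10.0 lists under the primary outcome.

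**The opposite assumption.** If 80% was calculated for 10 v 10 (d = 1.325), 16 v 10 has 88% power.

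**Which total does the interim rule fit?** Information is proportional to n₁n₂/(n₁ + n₂): 2.5 for 5 v 5, 5 for 10 v 10, and 6.154 for 16 v 10. The look is therefore at 2.5/5 = 50% of a 10 v 10 design, or 2.5/6.154 = 41% of a 16 v 10 design. The two-look O'Brien-Fleming first bound is 2.797 at 50% and 3.09 at 41%. The stated 2.80 matches 50%. The total of 30, the look at 5 per group and the bound all fit 10/10/10, whereas the sample-size bullet does not.

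**The case against.** Only the 36 v 30 mismatch is certain. The 70% figure needs three things that the documents do not say: that enrolment stops at 30, that the 30 are split equally, and that 80% is exact at 16 v 10. Group sizes are often rounded up. If 16 v 10 really gave 85%, 10 v 10 would give 76%; at 90% it would give 82%. This stands, so 70% is one labelled scenario and not a finding about the study.

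The mismatch may also be benign. The timeline bullet looks like a 10/10/10 schedule that was not revised when the T1DM group was set at 16. In that case 36 governs and the power statement is sound. This is plausible, but it is inference, and the current text leaves both totals in force.

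The sample size is openly adjustable after the interim look, so the 12 for year 2 is provisional. That weakens any claim that the study would finish at 30. It does not reconcile the totals, because the adjustment depends on a variance not yet seen, while the two totals differ before any data exist.

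The interim bound matters little. With 2.80 at 41% information and an assumed final bound of 1.977 (the plan gives none), the two-sided type I error is 5.06%, against 5.00% at 50%. This also stands: the bound is something to check and adds no weight to the point.

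**Conclusion.** The point holds. Section 10.0 states two incompatible totals, 36 and 30, and nothing in the documents reconciles them. That part is plain arithmetic and needs no assumption.

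The consequence for power is conditional. If 80% is exact at 16 v 10 and the study ends at 10 per group, power for the 40% difference is about 70% (69% to 71% across two-sided methods), and the detectable difference is about 45%. If the 80% belongs to 10 v 10, a study of 30 has the stated power. The documents do not show which applies, and they do not say that enrolment stops at 30. It must be corrected because the total and the power are basic design figures, and they contradict each other as written.

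**What to change.** State one total in section 10.0, with its split by group, and make the rest of the section agree with it.

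- **If 36 stands:** change the yearly figures so that they sum to 36 (for example 18 + 18), and check the interim bound against a look at about 41% of the information.
- **If 30 stands and the 80% was calculated for 16 v 10:** restate the group sizes and the matching power. At 10 v 10 that is about 70% for a 40% difference, or a detectable difference of about 45%, to be recalculated with the actual SD.
- **If the 80% was calculated for 10 v 10:** say so and correct the sample-size bullet.

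In every case, give the R_d mean and SD used so that the power can be checked.

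The cost is wording in section 10.0. If 36 stands, one yearly figure changes and possibly the bound. If 30 stands with the 80% tied to 16 v 10, the stated power becomes less favourable.

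### The early-stopping rule cannot be met with the Mann-Whitney test at 5 per group, its bound assumes half the information, and the section gives two totals (36 and 30)

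*Combined protocol and SAP*

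**What the plan says.** Everything is in section 10.0, Statistical Considerations.

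- **Test.** Differences in R_d "between MODY2 and T1DM subjects will be evaluated using the Mann-Whitney U test, presuming a non-parametric distribution in the data". No other test is named for R_d, at the interim or at the end.
- **Group sizes.** The sample-size item gives "10 per control group, 16 per T1DM group, and 10 per MODY2 group".
- **Accrual.** The timeline item says "I plan to study 18 subjects in year 1 and 12 additional subjects in a second year of funding".
- **Interim look.** One assessment of R_d "will be made after 5 studies per group before the end of the year 1 funding period".
- **Stopping rule.** Two-sided 5% O'Brien-Fleming bounds, where "a critical z-value of 2.80 (corresponding to a p-value of 0.0051) will be used to assess whether the study can be ended".
- **Re-estimation.** After the look the investigator will review the variance of R_d and "adjust the sample size if needed for subsequent studies in year 2".

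The section states no information fraction, no final critical value and no separate interim test.

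**The concern.** A rank test on very small groups has a floor below which its p-value cannot fall, however large the true difference. If that floor lies above the stopping threshold, the early stop exists only on paper. The bound of 2.80 also has to match the fraction of information available at the look, and that fraction depends on the final group sizes, for which the section gives two incompatible totals.

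The practical stake is that the plan promises an early end for a large T1DM v MODY2 difference and cannot deliver it. Each further subject has an overnight stay and a clamp with an investigational somatostatin infusion, and is asked for two muscle biopsies (sections 6.2.2 and 7.4). Some are adolescents (section 7.6). If the problem is found only at the look, a test or threshold would have to be chosen with the data in view.

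**Working it through.** **Inputs, all from section 10.0.** Mann-Whitney U test; look at 5 MODY2 v 5 T1DM; bound z = 2.80, p = 0.0051; final sizes 10 MODY2, 16 T1DM, 10 control; accrual 18 + 12. No mean or SD of R_d is given, so standardized differences d below are assumptions.

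**1. The plan's own figure.** The two-sided normal p-value for z = 2.80 is 0.0051, as stated. The classical two-look O'Brien-Fleming design sets the interim bound at c/√t and the final bound at c, with c chosen so that overall two-sided error is 5%. At t = 0.50 this gives 2.797 at the look and 1.977 (p = 0.048) at the end. So 2.80 and 0.0051 agree with each other and are the values for a look at half the information.

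**2. Can Mann-Whitney reach it at 5 v 5?**
- Exact: there are C(10,5) = 252 rank allocations. Complete separation in either direction gives p = 2/252 = 0.0079, the smallest possible value.
- Normal approximation: z = (nm/2)/√(nm(n+m+1)/12) = 12.5/√(25·11/12) = 12.5/4.787 = 2.61. With continuity correction, 12/4.787 = 2.51.

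None of the 252 allocations gives z ≥ 2.80 or p ≤ 0.0051. This needs no assumption about effect size or SD, only untied data, which is realistic for a continuous rate.

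**3. Information at the look.** For two groups, information is proportional to n₁n₂/(n₁+n₂).

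| Look | Final | Fraction | Interim bound |
|---|---|---|---|
| 5 v 5 | 10 v 16 | 2.5/6.154 = 40.6% | 3.09 (p 0.0020) |
| 5 v 5 | 10 v 10 | 2.5/5.0 = 50% | 2.80 |
| 5 v 8 | 10 v 16 | 3.077/6.154 = 50% | 2.80 |
| 6 v 6 | 10 v 10 | 3.0/5.0 = 60% | 2.57 (p 0.0101) |

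**4. Totals.** 10 + 16 + 10 = 36; 18 + 12 = 30. The 5 per group and the 12 additional subjects fit 30. But 18 is also half of 36, and splitting 18 as 5/8/5 gives exactly 50% information and hence 2.80. The text does not settle which was meant.

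**5. What this costs** (normal data, equal SDs). d = 1.18 gives 80% t-test power at 10 v 16; d = 1.325 does so at 10 v 10.
- At d = 1.18, complete separation at 5 v 5 occurs in about 11% of studies, and none of them would stop.
- Looks that can work: 5 v 8 with p ≤ 0.0051 stops about 9% of the time at d = 1.18 (6% to 18% for d from 1.0 to 1.5). 6 v 6 with p ≤ 0.0101 stops about 22% at d = 1.325 (11% to 30% over the same range). At a common d = 1.18 the two rates are about 9% and 17%.
- Mann-Whitney power at d = 1.225: 80.0% at 10 v 16, 68.8% at 10 v 10.

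**The case against.** **The look might not be exactly 5 v 5.** Five per group could be read as a minimum. T1DM patients are plentiful at the site, and with 7 or 8 of them against 5 MODY2 the maximum z is 2.84 or 2.93, so the bound could be crossed. That is possible but not the natural reading, and a stopping rule should not depend on it.

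**The interim sentence names no test, and a z-value may imply a parametric one.** Carrying Mann-Whitney over is an inference, but the look is at the primary outcome and the plan gives no other test for it. A t-test would not rescue the rule as written. On 8 df, |t| = 2.80 has nominal p = 0.023, whereas p = 0.0051 needs |t| ≥ 3.82. At d = 1.18 these two versions stop about 24% and 9% of the time, so the rule would still be ambiguous.

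**The information mismatch is conditional and small.** This is fair. The 40.6% applies to the stated 10 v 16; with 10 v 10 the 2.80 is correct. Under normal theory, 2.80 at 40.6% followed by 1.977 gives overall error of 0.0506. Under Mann-Whitney at 5 v 5 the look spends nothing.

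**The sample size may be adjusted anyway.** That permission applies after the look. It does not explain why the two planned totals differ beforehand.

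**The loss is minor.** This stands for the stop itself: even a workable look would seldom end the study. It does not stand for the total.

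**Conclusion.** The concern holds. Under the only test named, and with exactly 5 untied values per group, the chance of stopping at the look is zero whatever the true difference. The bound fits half the information, not the 40.6% that 5 v 5 represents of 10 v 16. The planned totals of 36 and 30 conflict, and the documents do not show which is intended.

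The unreachable stop is conservative: it does not inflate type I error, reduce final power or threaten the primary result. The conflict over the total carries more weight, because 10 v 10 instead of 10 v 16 would cost about 11 percentage points of power. That figure assumes that 30 means 10 per group, normal data with equal SDs, and d = 1.225. The section should be corrected before the look, but the defect does not invalidate the study.

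**What to change.** First state one total and one set of group sizes, with year-1 and year-2 numbers that add to it (36 would need 18 + 18). Then choose one of two routes.

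1. **Remove the efficacy stop** and test the final analysis at two-sided 5%.
2. **Keep it, with a look that can cross the bound**, stated as an exact Mann-Whitney p-value and with the final level written down:
   - Final 10 v 16: look at 5 MODY2 v 8 T1DM. Stop if exact p ≤ 0.0051, that is U ≤ 1 or ≥ 39 (p = 4/1287 = 0.0031; U ≤ 2 would give 0.0062). Final p ≤ 0.048.
   - Final 10 v 10: look at 6 v 6. Stop if exact p ≤ 0.0101, that is U ≤ 2 or ≥ 34 (p = 8/924 = 0.0087; U ≤ 3 would give 0.0152). Final p ≤ 0.046.

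The rule should not be written as z. At 5 v 8, U = 1 has exact p = 0.0031 but z = 19/6.831 = 2.78, so a z rule and a p rule would disagree.

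**Cost.** Route 1 is wording only. Route 2 is a slightly later look; 5/8/5 and 6/6/6 both use the 18 subjects planned for year 1. The final critical U is the same as at 0.05: 42 for 10 v 16 (p = 0.0467) and 23 for 10 v 10 (p = 0.0433). Simulated overall error is 4.8% and 4.7% respectively. Settling the total has its own cost: 36 means six more subjects than the accrual plan, while 30 as 10 per group means the lower power given above.
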